4.1.15 Follow-up for Withdrawn Subjects

If a subject withdraws from the study, any recorded data will still be included in the analysis. Subjects will only be replaced if they withdrew prior to undergoing PAE.

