8.2 Sample Size Rationale

Prior studies have demonstrated larger decreases in IPSS scores using PAE, compared to medication alone. Abt found the mean decrease in IPSS to be 9.23 for PAE with standard deviations of IPSS scores being 5.7 at baseline and after treatment (18). Lepor found a decrease in IPSS attributable to medications of 6.6 (17).

We set a 10% non-inferiority margin and expect the correlation of IPSS scores between screening and 6-months to be high. Assuming a correlation of .65 we will have 81.2% power to test the non-inferiority hypothesis with an alpha of 0.025 for our 30 budgeted pairs, assuming 20% dropout (pairs=subjects given single subject study design).

Power calculations used PROC POWER, SAS, Version 9.4. This sample size is adequately large to address the study's primary aim with reasonably large power.

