8.3 Data Analysis Plans

A patient will be considered an evaluable study subject evaluable for data analysis per the following criteria, a written informed consent was obtained, he meets the inclusion and exclusion criteria, and received the PAE study procedure. All subjects with 12-month follow-up data will be included for analysis even if some follow up data is incomplete. Every attempt will be made to ensure that there is as

little missing data as possible including reminder phone calls and follow-up phone calls, if a subject misses a visit.

The primary aim is to demonstrate non-inferiority of PAE compared to medication with respect to the outcome measure IPSS. We assumed a non-inferiority margin of 10%, in line with the FDA's recommendations, since similar prior non-inferiority trials were unavailable. The null hypothesis states that in the target population mean IPSS is at least 10% greater at 6 months post-treatment than at baseline (pre-treatment). The alternative hypothesis will be that the mean IPSS at 6 months is less than or equal to 10% greater than the mean IPSS at screening.

To address this hypothesis we will implement a random effects linear model, modeling IPSS score as a function of time and the indicator of whether medication had stopped by the time of the 3-month follow-up. We will include an R-side compound symmetric random effect to account for patient-level correlation. We will compute the predicted mean and standard deviation(SD) of IPSS at screening and 6 months; the difference of the predicted mean IPSS score, defined as the mean IPSS at 6 months minus the mean IPSS at screening; and the SD of this difference. Point estimates of these values will be reported along with 95% confidence intervals for the mean difference.

A non-inferiority p-value <0.05 testing whether the difference in the predicted mean at screening is at least 10% greater than the predicted mean of IPSS at screening will be considered evidence against the null hypothesis of inferiority of PAE, compared to treatment. A non-inferiority p-value >0.05 will be considered inconclusive evidence against inferiority.

As a sensitivity analysis for the primary aim, we will repeat the same model outlined above after removing patients from the analysis who were still taking medications at the 3-month follow-up. Point estimates, confidence intervals, and p-values will be compared against those obtained in the primary analysis.

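### The primary model needs a 3-month medication status for every man, and the plan has no rule for a man whose status is unknown; a standard fit would drop all his IPSS scores

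*Combined protocol and SAP*

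**What the plan says.** Section 8.3 describes the primary analysis as a linear model of IPSS on time and on "the indicator of whether medication had stopped by the time of the 3-month follow-up". The covariance is compound symmetric within patient: "We will include an R-side compound symmetric random effect to account for patient-level correlation". The primary contrast is "defined as the mean IPSS at 6 months minus the mean IPSS at screening".

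The indicator takes one value per man. Its scheduled source is the medication history questionnaire at Visit 5 (4.1.10). The questionnaire is repeated at Visit 6 (4.1.11 and the table in 4.3).

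Four statements bear on who stays in the analysis:

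- 4.1.14 announces an intent-to-treat analysis.
- 4.1.15 says of men who withdraw that "any recorded data will still be included in the analysis". Only men who withdraw before the procedure are replaced.
- 8.3 calls a man evaluable if he consented, met the eligibility criteria and received PAE. Attendance at Visit 5 is not a condition.
- 8.3 also says that men with 12-month data will be "included for analysis even if some follow up data is incomplete".

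Section 8.2 plans for 30 men, "assuming 20% dropout". Nothing in 8.3 or 9.4.2 says how an unknown medication status enters the model. Section 9.4.2 covers prevention and documentation of missing data only. The sensitivity analysis in 8.3 removes men known to be still on medication at month 3 and does not mention unknown status.

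**The concern.** The covariate arises after treatment and can be missing for two kinds of men. One withdraws before Visit 5 and has only a screening IPSS. The other skips Visit 5 but returns later, so his 6-month IPSS is measured. Standard mixed-model software leaves out any record with a missing covariate. Because the indicator is constant within a man, all his records go.

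This would matter in two ways. A man with a measured primary endpoint could be lost through a gap in a covariate. The model would also give up its main advantage with incomplete follow-up, which is that screening scores of early leavers protect the contrast when leaving depends on those scores. With 30 men and a planned power of 81.2%, this should not be left to a software default.

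**Working it through.** **Inputs from 8.2.** SD 5.7 at both times; correlation 0.65; one-sided alpha 0.025; mean IPSS decrease 9.23 (PAE) and 6.6 (medication), a difference of 2.63; 30 men with 20% dropout, leaving 24 pairs.

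**Plan's own power.** SD of the paired difference = 5.7 × √(2 × (1 − 0.65)) = 4.769. The stated power is reproduced by a margin of 10% of 2.63 = 0.263, so the distance from the null is 2.63 + 0.263 = 2.893. With 24 pairs the noncentrality is 2.893 / (4.769/√24) = 2.97, and the noncentral t gives 81.2%, as stated.

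**Does the indicator help the contrast?** In one simulated complete data set of 30 men and four visits, the 6-month-minus-screening contrast was −2.973 (SE 0.871) with the additive indicator and the same without it. A per-man main effect moves all of a man's visits equally and cancels from the difference.

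**Precision.** Assume six of 30 men lack status. The number six matches the 20% in 8.2, but 8.2 does not say when dropout occurs. If all 30 screening scores are kept and m men also have a 6-month score, under compound symmetry

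SE² = 5.7² × [(1 − 0.65²)/m + (1 − 0.65)²/30].

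| Handling of the six men | m | SE |
|---|---|---|
| All six deleted (4.769/√24) | – | 0.973 |
| Kept; all six left before Visit 5 | 24 | 0.956 |
| Kept; three left, three missed only Visit 5 | 27 | 0.910 |
| Kept; all six missed only Visit 5 | 30 | 0.871 |

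Deletion therefore inflates the SE by about 2%, 7% or 12%.

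**Bias.** If missing status depends only on screening IPSS, deletion moves the retained screening mean by some amount δ. The 6-month mean moves by 0.65δ, so the contrast is biased by −0.35δ. Simulation used a true change of −2.6, an assumed screening mean of 19, and six men leaving before Visit 5:

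| Log-odds of leaving per SD of screening IPSS | Bias from deletion | Bias with all scores kept |
|---|---|---|
| 0 | about 0 | about 0 |
| 0.5 | about 0.2 | about 0 |
| 1 | about 0.4 | about 0 |

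At slope 1 the screening mean falls from 19.0 to 17.9, and −0.35 × (−1.1) = 0.385 agrees with the simulation. A margin of 10% of that mean falls by 0.11. If men with milder symptoms leave, the sign reverses. A negative bias also arises if men with high 6-month scores skip Visit 5.

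**Power.** On the 8.2 inputs, deleting all six leaves 24 pairs and the planned 81.2%. Keeping three who missed only Visit 5 gives 27 pairs: noncentrality 2.893 / (4.769/√27) = 3.15, power about 85.9%.

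**The case against.** The strongest reply is that no sentence in the plan deletes anyone. Deletion is what software does by default, whereas the written rules point the other way. This stands: the plan has a gap, which becomes a conflict only if the default is used. A reader might infer that 8.3 contradicts 4.1.15 outright, and the text does not support that.

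Second, many statuses can be recovered. The indicator asks whether medication had stopped by month 3, which a man can still answer at Visit 6. Staff also ask about therapies during follow-up (4.1.13), and missed visits trigger calls (8.3, 9.4.2). This stands too, but no rule tells the analyst to use those sources. The men whose status is truly lost mostly have only a screening score, and keeping that adds little precision (0.956 against 0.973).

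Third, a reader might infer that the primary contrast is biased. That needs missing status to be related to IPSS, and the documents give no evidence of how men will be lost. When higher-scoring men leave, the bias also works against PAE.

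Fourth, a reader might infer that power drops from 81.2% to 75.3%, the value for 21 pairs. That counts dropout twice, because 24 pairs already allows for six lost men.

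Finally, the 8.3 sentence on incomplete follow-up covers only men with 12-month data, so it does not protect a man who withdraws early. His protection comes from 4.1.14, 4.1.15 and the evaluable definition.

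**Conclusion.** The point holds as a gap in the primary analysis, and it is worth fixing. The model in 8.3 depends on a value that can be missing, no rule covers that case, and the usual fit would then remove men whom the plan's inclusion statements keep.

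The cost is modest and conditional. With six of 30 statuses unknown, it is between 2% and 12% in standard error, and at most the forgone gain in power from the planned 81.2% (about 85.9% if three of the six can be kept). Bias runs from nil to roughly 0.4 points over the slopes examined, in either direction. These figures rest on the SD and correlation in 8.2 and on assumed numbers and patterns of missing status; the bias figures also assume how leaving depends on screening IPSS. The power figures use the 0.263-point margin that reproduces 8.2. With a margin of 10% of an assumed screening mean of 19 (1.9 points), power is about 99% at 24 pairs, and the power argument has little force.

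What makes the change worthwhile is that the indicator gives the primary contrast nothing when data are complete, so the plan carries this risk without a return.

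**What to change.** In 8.3:

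- Fit the primary model with visit only, using every recorded IPSS of every evaluable man, and say that no man is removed for an unknown medication status.
- Use medication status only in the sensitivity analysis. Where the Visit 5 status is missing, derive it from the Visit 6 medication history if available.
- Report the number of men whose status remains unknown.
- Reconcile the sentence on men with 12-month data with the evaluable definition and with 4.1.14 and 4.1.15, so that one inclusion rule governs.

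If the sponsor prefers to keep the indicator, a prespecified derivation rule would restore the recoverable men. Adding an unknown category is a weaker substitute. In the three-and-three pattern it gave SE 0.913 and cut the bias from about 0.38 to 0.15. When all six men have only a screening score, it gives the same result as deletion.

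The cost is a few sentences and no new data. The medication-adjusted model becomes secondary, and a status derived at Visit 6 relies on recall.

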3.1.3 Prostate gland measures \geq 50 grams measured by MRI, CT, or ultrasound

3.1.4 Currently taking BPH medications including either alpha blockers, 5-alpha reductase inhibitors or the combination of both for no less than 6 months

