4.1.4 Prior and Concomitant Therapy

The subjects will be required to have been on medical therapy for BPH for at least six months prior to undergoing PAE. Such medications include alpha blockers, 5-ARIs or combination therapy. The medication usage will be stopped by the 3 month visit in order to allow an adequate washout period for 5-ARI's prior to the 6 –month visit.

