4.2.2 Effectiveness Assessments

Technical success will be defined as bilateral prostatic artery embolization. This will be determined during the procedure. Clinical success will be defined as an IPSS score reported at the 6-month visit that is equal to or less than the pre-PAE baseline score. The size of the prostate will be measured by MRI at 6-month follow-up visit. IPSS, QoL, PVR and Qmax will be measured at 3, 6 and 12-month follow-ups.

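### If several post-PAE visits enter the primary model, compound symmetry misstates the standard error of the 6-month-minus-screening contrast unless the pairwise correlations happen to average to the screening-to-6-month value

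*Combined protocol and SAP*

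**What the plan says.** The primary analysis in section 8.3 is a linear model "modeling IPSS score as a function of time and the indicator of whether medication had stopped by the time of the 3-month follow-up". Its covariance is fixed in one sentence: "We will include an R-side compound symmetric random effect to account for patient-level correlation". The primary quantity is the difference in predicted means, "defined as the mean IPSS at 6 months minus the mean IPSS at screening", reported with a 95% confidence interval and a non-inferiority p-value. Section 8.3 names no other covariance structure, no robust standard error and no check of the structure. The one sensitivity analysis refits the same model after removing men still on medication at 3 months.

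On the data that could enter the model, section 4.2.2 states "IPSS, QoL, PVR and Qmax will be measured at 3, 6 and 12-month follow-ups", and the Time and Events Table (4.3) adds screening. Screening is on drug (section 3.1.4: "Currently taking BPH medications including either alpha blockers, 5-alpha reductase inhibitors or the combination of both for no less than 6 months"). Section 4.1.4 says of the period after PAE: "The medication usage will be stopped by the 3 month visit". Section 8.3 does not say which visits are modelled or whether time is categorical.

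For sample size, section 8.2 uses "standard deviations of IPSS scores being 5.7 at baseline and after treatment" and, for screening to 6 months, "Assuming a correlation of .65". No correlation between post-PAE visits is given anywhere.

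**The concern.** Compound symmetry imposes one variance and one correlation on every pair of visits. With four visits there are six pairs: three link screening to a post-PAE visit and three link post-PAE visits to each other. Screening is taken before PAE and on drug. The later scores all follow PAE and share each man's response to it, so they may correlate more closely with each other than with screening.

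The primary contrast depends on one pair only, screening and 6 months. A model that pools all six correlations uses the wrong value for that pair unless the average equals it. If the pooled value is too high, the standard error is too small and the error favours declaring non-inferiority. If it is too low, the test loses power. The sensitivity analysis keeps the same covariance and would not reveal either problem.

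**Working it through.** **Inputs from the plan.** SD 5.7 at both times, correlation 0.65, mean decreases of 9.23 (PAE) and 6.6 (medication), 10% margin, alpha 0.025, 30 men with 20% dropout (all section 8.2), so n = 30 × 0.8 = 24. **Assumed.** The correlation between post-PAE visits, ρp; 0.65 for all three screening-to-post pairs (ρs); complete data; categorical visit.

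**The plan's own power figure.** SD of the paired difference = 5.7 × √(2 × (1 − 0.65)) = 4.769; SE = 4.769/√24 = 0.973. A one-sided paired t-test at 0.025 with 23 df and a detectable difference of 1.1 × (9.23 − 6.6) = 2.893 gives 81.2%, the stated value. The planned power therefore comes out as that of a paired test using the screening-to-6-month correlation alone.

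**What compound symmetry uses instead.** With four complete visits and equal SDs it estimates the mean of the six correlations, (3ρs + 3ρp)/6 = (ρs + ρp)/2.

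- True SE = SD × √(2(1 − ρs)/n)
- Model SE = SD × √(2(1 − (ρs + ρp)/2)/n)

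For ρp = 0.80, the average is 0.725 and the model SE is 5.7 × √(2 × 0.275/24) = 0.863, against a true 0.973: ratio 0.89.

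Error rates and coverage below are from 40,000 simulated trials per case, with 3 × 23 = 69 df for compound symmetry:

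| ρp (assumed) | Model SE | Ratio to true SE | One-sided error at 2.5% | At 5% | 95% CI coverage |
|---|---|---|---|---|---|
| 0.75 | 0.901 | 0.93 | 3.6% | 6.5% | 93% |
| 0.80 | 0.863 | 0.89 | 4.0% | 7.1% | 92% |
| 0.85 | 0.823 | 0.85 | 4.8% | 8.2% | 90% |

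Both nominal levels are shown because section 8.2 uses 0.025 while section 8.3 tests at 0.05. At ρp = 0.65 the two SEs agree and the error is 2.5%. A normal approximation, 1 − Φ(1.96 × ratio), gives 3.5%, 4.1% and 4.9% for the three rows, in line with the simulation. The paired contrast, which is what an unstructured model gives with complete data, stayed at 2.4 to 2.6%. A larger sample does not help: at n = 30 and ρp = 0.80 the error is still 4.0%.

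**Conditions that change the answer.**

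- Lower post-PAE correlation: at ρp = 0.55 the ratio is √(0.40/0.35) = 1.07 and the simulated error about 1.9%, so the test is conservative.
- Three visits (screening and two post-PAE) with ρp = 0.80: average (0.65 + 0.65 + 0.80)/3 = 0.70, ratio 0.93, error about 3.5%.
- Screening and 6 months only: one pair, ratio 1.00, no bias.
- Decaying correlations (assumed): screening with 3, 6 and 12 months 0.75, 0.65, 0.55; then 3–6, 6–12 and 3–12 months 0.70, 0.70, 0.60. The average is 3.95/6 = 0.658 and the ratio √(0.342/0.35) = 0.99. With 0.70, 0.65, 0.60 and 0.75, 0.75, 0.70 the average is 4.15/6 = 0.692 and the ratio 0.94.
- Unequal SDs (assumed): with ρp = 0.80 and a post-PAE SD of 7.0 or 4.5 the ratio is 0.91 or 0.84; with SD 7.0 and ρp = 0.65 it is 1.03.

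**The case against.** The strongest reply is that the plan may not have the problem at all. Section 8.3 asks for predicted means at screening and 6 months only, and section 8.2 counts pairs. If just those two visits are modelled, compound symmetry gives exactly the paired standard error. This stands as a condition. The multi-visit reading is the more natural one, because IPSS is modelled as a function of time and section 8.3 admits men with 12-month data even when some follow-up is incomplete, but the text does not settle it.

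Second, the size rests on post-PAE correlations that the documents do not give, and a clean split between screening and later visits may be too simple. Medication stops only by month 3, section 4.1.10 foresees men unable to stop, and the questionnaire in Appendix 12.1 covers the past month. The 3-month score may therefore resemble the on-drug screening score more than the two-block calculation allows. This also stands, and is why the decaying patterns, with a bias of 1 to 6%, belong in the range.

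Third, the calculation leaves out the medication-stopped indicator. As a main effect fixed for each man, it cancels from his 6-month-minus-screening difference, so with complete data the comparison is unaffected. An interaction with time would change that.

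Finally, compound symmetry is a prespecified, parsimonious choice for 24 to 30 men, and with complete data the point estimate does not depend on it. Both are true, but neither repairs the standard error.

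**Conclusion.** The point holds conditionally. If the primary model includes screening and more than one post-PAE visit, its standard error for the primary contrast is calibrated only when the pooled correlation equals the screening-to-6-month one, and nothing in the plan supports that equality. Under the stated assumptions the standard error is 7 to 15% too small for post-PAE correlations of 0.75 to 0.85, with one-sided error of about 3.6 to 4.8% at nominal 2.5% and 6.5 to 8.2% at nominal 5%.

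A reader might infer that the false-positive rate is inflated as a matter of fact, or that the interval must be wrong in one direction or the other. The documents support neither. The correlations that drive the bias are unknown, its direction can reverse, and it vanishes if the correlations are equal or only two visits are modelled. The case for change is that the alternative is valid under any correlation pattern and costs little.

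**What to change.** In section 8.3, list the visits in the model (screening, 3, 6 and 12 months if that is the intention), treat visit as categorical, and take the primary contrast from a model with an unstructured R-side covariance and Kenward-Roger degrees of freedom.

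Name a fallback for non-convergence: the paired 6-month-minus-screening change, or compound symmetry with a small-sample-corrected sandwich standard error. Heterogeneous Toeplitz is not suitable. It forces the screening-to-6-month correlation to equal the 3-to-12-month one, and for post-PAE correlations of 0.75, 0.80 and 0.85 its SE ratios are 0.94, 0.91 and 0.89, so most of the defect remains.

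The cost is SAP wording and a model option. The covariance has 10 parameters instead of 2, and the contrast about 23 df instead of 69. If compound symmetry is in fact true, the interval is about 4% wider (t quantiles 2.069/1.995 = 1.037) and power is about 81.2% instead of 83.4%. The plan claims only 81.2%, which was reproduced as a paired test, so the stated power and the 30 men are unaffected. No visit or patient procedure changes.

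### The margin is 10% of a screening mean estimated in the same men, but 8.3 defines only the plain difference and its error and never writes the test; on the natural reading the standard error is about 5% too small

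*Combined protocol and SAP*

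**What the plan says.** All of this is in the combined protocol and SAP.

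- **Margin.** Section 8.2 opens the power statement with "We set a 10% non-inferiority margin and expect the correlation of IPSS scores between screening and 6-months to be high". Section 8.3 makes the 10% relative to baseline: under the null, "mean IPSS is at least 10% greater at 6 months post-treatment than at baseline (pre-treatment"). The decision rule ties it to a model estimate, asking whether a quantity "is at least 10% greater than the predicted mean of IPSS at screening". Neither section gives a margin in IPSS points or an expected screening mean.
- **Quantities computed.** Section 8.3 says "We will compute the predicted mean and standard deviation(SD) of IPSS at screening and 6 months". It then adds the difference, "defined as the mean IPSS at 6 months minus the mean IPSS at screening; and the SD of this difference", and "95% confidence intervals for the mean difference".
- **Model.** A linear model for IPSS on time and an indicator of medication stopped by 3 months, with an "R-side compound symmetric random effect to account for patient-level correlation".
- **Test.** A non-inferiority p-value is compared with 0.05. The statistic behind it, its standard error and its sidedness are not given, and the sentence that describes the p-value is garbled.

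**The concern.** Write μ0 and μ6 for the mean IPSS at screening and at 6 months (higher is worse). The null is μ6 ≥ 1.1 μ0. The margin, 0.1 μ0, is unknown and is estimated from the same men as the change.

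If the estimated change is judged by its own error against 0.1 times the estimated screening mean, the margin's sampling error is ignored. That error does not cancel. A screening mean that is high by chance makes the change look more favourable and also widens the margin, so it helps PAE twice. The test would then declare non-inferiority at the boundary more often than its nominal level.

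This is the trial's single primary decision. With the statistic unwritten, the standard error could also be chosen after the data are seen.

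**Working it through.** **Inputs.** From 8.2: SD 5.7 at both times, correlation r = 0.65, 30 pairs with 20% dropout (30 × 0.8 = 24), alpha 0.025, decreases of 9.23 (PAE) and 6.6 (medication). From 8.3: the 10% relative margin and compound symmetry, which implies equal variances. Assumed: screening means of 12, 15 and 20 in the simulation, because the documents give none.

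**1. The plan's own figure.** The SD of the plain difference is 5.7 × √(2 − 2 × 0.65) = 5.7 × √0.70 = 4.769. With n = 24 and a one-sided paired t-test at 0.025, a distance of 1.1 × (9.23 − 6.6) = 2.893 gives 81.2% power, as stated. The plan does not print this distance; it is inferred from the match. The reproduced power therefore uses the plain-difference SD and a distance that is not built from 10% of a screening mean.

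**2. Two variances** (common SD s, n men):

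- Plain difference: s²(2 − 2r)/n. At r = 0.65 the factor is 0.70.
- Quantity in the hypothesis, the 6-month mean minus 1.1 times the screening mean: s²(1 + 1.21 − 2.2r)/n. At r = 0.65 the factor is 2.21 − 1.43 = 0.78.
- Gap: s²(0.21 − 0.20r)/n, which is positive for every correlation when the SDs are equal.

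**3. Standard errors at n = 24.** Plain: 4.769/√24 = 0.973. Correct: 5.7 × √0.78 = 5.034, and 5.034/√24 = 1.028. The ratio is √(0.70/0.78) = 0.947, so the plain error is 5.3% too small (the correct one is 5.6% larger).

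**4. Error rate at the boundary.** If the plain error is used, the rate is P(T > 0.947 × t_crit), with 23 or 29 degrees of freedom.

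| r (equal SDs) | nominal 2.5% | nominal 5% |
|---|---|---|
| 0.3 | 3.1% | 5.9% |
| 0.65 | 3.1% | 5.9% |
| 0.9 | 3.3% | 6.2% |

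The normal approximation at r = 0.65 gives 3.17% and 5.96%.

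**5. Simulation** (400,000 trials per setting, n = 24 and 30, r = 0.65). The plain error gave 3.1–3.2% and 5.9–6.0%. The contrast with its own error gave 2.5–2.6% and 5.0–5.1%. The assumed screening mean made almost no difference.

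**6. Unequal SDs.** Let q be the 6-month SD divided by the screening SD. The variance gap is proportional to 0.21 − 0.20rq. At r = 0.65 it is zero at q = 0.21/0.13 = 1.6. Rates at nominal 2.5% (normal approximation):

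| q | 0.8 | 1.0 | 1.2 | 1.4 | about 1.6 |
|---|---|---|---|---|---|
| rate | 3.5% | 3.2% | 2.9% | 2.6% | 2.5% |

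**7. Power cost.** With the distance 2.893 held fixed, n = 24 and one-sided 0.025, replacing 4.769 by 5.034 lowers power from 81.2% to 76.9%. This is illustrative, because the distance is inferred.

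**The case against.** The strongest reply is that the plan never says it will use the plain-difference error in the test. A reader might infer that it computes nothing else, so that the primary decision is bound to exceed its nominal level. The documents do not support that. Section 8.3 also computes SDs of both predicted means. If these are errors of the means, then together with the SD of the difference they give the covariance, and hence the correct variance. The sentence on the difference lists what will be reported; the p-value is described in another paragraph that names no statistic. A contrast with weights 1 and −1.1 from the same model is compatible with the text. This part of the reply stands: the inflation is conditional on how the test is run.

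Three further points stand in part.

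- **The effect is small and depends on equal SDs.** True, but 8.2 assumes equal SDs and the compound-symmetric model imposes them. The calculation is a paired test, not the full model with its covariate.
- **The alpha conflict is larger.** Section 8.2 uses 0.025, while 8.3 uses p < 0.05 without sidedness. That is a separate issue, and settling it does not remove this one.
- **The planned interval is still useful.** A reader might infer that the 95% interval for the change is invalid. It is a valid interval for the mean change. Setting its upper limit against the estimated margin gives about 3.1% rather than 2.5%, which is still below 5%.

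**Conclusion.** The point holds in conditional form. The margin is a fraction of an estimated mean, the only comparison 8.3 defines is the plain difference with its SD and interval, and the test is not written. An analyst who follows the text would most naturally use an error that is about 5% too small. Under equal SDs and r = 0.65, that gives about 3.1% false non-inferiority at a nominal 2.5% and 5.9% at a nominal 5%, one-sided.

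Under the planned equal-variance model the direction is certain. If the true SDs differ, the excess grows when the 6-month SD is the smaller and is gone at a ratio of about 1.6. The inflation is modest, but it bears on the primary decision and is cheap to remove.

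**What to change.** In 8.3, state that non-inferiority is tested by the single model contrast θ = μ6 − 1.1 × μ0, with its own model-based standard error, and is declared if the upper confidence limit of θ at the single pre-set alpha is below 0. Report θ and that limit beside the plain mean difference.

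State also that the medication-stopped indicator is averaged at its observed mix. As a main effect it cancels from the plain difference, but it enters θ with weight 1 − 1.1 = −0.1, so the result depends on how it is averaged.

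The cost is a short addition to 8.3 and one contrast in the code, with no new data. The test becomes slightly harder to pass (illustratively, 81.2% to 76.9% power at 24 men), so the power in 8.2 should be recomputed for this contrast with a stated screening mean. The alpha conflict between 8.2 and 8.3 must be settled separately.

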To address the secondary aim, we will tabulate the proportion of patients AEs pre- and post-PAE, comparing the proportion using McNemar's test. A p-value <0.05 for McNemar's test will be considered evidence that the proportion of AE's differs for medication, compared to PAE. A p-value >0.05 will be considered inconclusive. We will assume that the adverse events that occur following PAE will be attributed to the procedure and not medication.

We will present the percentage of prostate infarcted at 6 months and the incidence of minor complications at 1 month descriptively, and calculate 95% confidence intervals. Post-acquisition segmentation software will be used to measure infarct volume.

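### The primary non-inferiority rule uses p<0.05 with sidedness unstated, against a sizing alpha of 0.025, and the sentence that states it leaves out the 6-month mean

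*Combined protocol and SAP*

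**What the plan says.** Section 8.2 (Sample Size Rationale) computes power "with an alpha of 0.025 for our 30 budgeted pairs", allowing for 20% dropout, and reports 81.2%. It does not say whether that alpha is one- or two-sided.

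Section 8.3 (Data Analysis Plans) contains four statements that bear on the primary test:

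- The null hypothesis is that "mean IPSS is at least 10% greater at 6 months post-treatment than at baseline". This has one direction.
- The estimated difference is "defined as the mean IPSS at 6 months minus the mean IPSS at screening".
- The interval: "Point estimates of these values will be reported along with 95% confidence intervals for the mean difference". No rule compares this interval with a margin.
- The decision: "A non-inferiority p-value <0.05 testing whether the difference in the predicted mean at screening is at least 10% greater than the predicted mean", where the reference is again the screening visit. A result that meets this counts against inferiority, and "A non-inferiority p-value >0.05 will be considered inconclusive evidence against inferiority". Sidedness is not given.

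For adverse events, section 8.3 uses the same threshold: "A p-value <0.05 for McNemar's test will be considered evidence" that the proportions differ, which is a two-sided question.

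**The concern.** There are two defects in one sentence.

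**Threshold.** A p-value for a one-directional non-inferiority null is naturally one-sided. On that reading the decision level is 0.05, twice the sizing level, and non-inferiority can be declared while the reported 95% interval still includes the margin. A two-sided p would agree with both the sizing alpha and the interval, but the plan does not say that p is two-sided. A one-sided p between 0.025 and 0.05 would therefore be a success on one reading and inconclusive on the other, and the choice could be made after the data are seen.

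**Contrast.** Read literally, the rule compares screening with screening. It matches neither the null hypothesis nor the difference defined just before it. It also leaves open how a margin of 10% of an estimated screening mean is handled: as a fixed number, or with its sampling error included in the test.

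This sentence alone decides whether the primary aim is met in a single-arm, non-blinded study.

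**Working it through.** The figures below use paired-t approximations, not the section 8.3 mixed model.

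**Inputs from section 8.2.** SD 5.7 at both times; correlation 0.65; 30 pairs with 20% dropout; alpha 0.025; mean IPSS decreases of 9.23 (cited PAE trial) and 6.6 (cited medication trial); 10% margin, base not stated.

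**1. Reproducing the stated power.**
- SD of the paired difference: 5.7 × √(2 × (1 − 0.65)) = 4.769.
- Analysable pairs: 30 × 0.80 = 24, so SE = 4.769/√24 = 0.973.
- Distance from the margin (inferred): 9.23 − 6.6 = 2.63, plus 10% of 2.63 = 0.263, giving 2.893.
- Noncentral t power, 23 df: 81.2% at one-sided 0.025, which matches the plan; 89.2% at one-sided 0.05.
- A two-sided test at 0.05 also gives 81.2%. The power figure supports a one-sided level of 0.025 in the sizing, but it cannot show which sidedness section 8.3 intends.

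**2. Gap between the rule and the interval, margin treated as fixed.** Critical values with 23 df are 1.714 (one-sided 0.05) and 2.069 (one-sided 0.025).
- One-sided p<0.05 needs the estimate 1.714 × 0.973 = 1.67 points below the margin.
- A 95% interval that excludes the margin needs 2.069 × 0.973 = 2.01 points.
- The band between them is 0.345 points.

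**3. The contrast that matches the section 8.3 null.** The null is mean(6 months) − 1.1 × mean(screening) ≥ 0.
- SD: 5.7 × √(1 + 1.21 − 2.2 × 0.65) = 5.034; SE = 5.034/√24 = 1.028.
- Band: (2.069 − 1.714) × 1.028, about 0.36 points.

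**4. Type I error at the null boundary.** Simulation with 24 pairs, 400,000 replicates and screening means from 10 to 25 (assumed, because the plan gives none):

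| Test | one-sided 0.025 | one-sided 0.05 |
|---|---|---|
| 1.1 × contrast | 2.5% | 5.0% |
| Estimated margin treated as fixed | 3.1–3.2% | 5.9% |

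**5. Power of the 1.1 × contrast, 24 pairs.** The distance is 2.63 + 0.1 × screening mean, with the true 2.63-point advantage assumed.

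| Screening mean (assumed) | one-sided 0.025 | one-sided 0.05 | Difference (points) |
|---|---|---|---|
| 10 | 92.2% | 96.3% | 4.0 |
| 15 | 97.0% | 98.8% | 1.7 |
| 20 | 99.1% | 99.7% | 0.6 |
| 25 | 99.8% | 99.9% | 0.2 |

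At the inferred sizing distance of 2.893 points, the same contrast has 76.9% power at one-sided 0.025. That distance implies a margin of about 0.26 points, whereas section 8.3 sets the margin at 10% of mean screening IPSS. The sizing and the tested hypothesis therefore appear to use different margins.

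**The case against.** The strongest reply is that the inflation is conditional. If p is two-sided, then p<0.05, the 95% intervals and the sizing alpha of 0.025 all agree. The McNemar rule uses the same threshold for a two-sided question, which suggests a house convention of two-sided 0.05. On that view the plan is unclear but its error rate is not doubled. This stands as a limit on the claim: 5.0% is the error rate on one reading only. It does not remove the defect, because the plan never states the reading that would reconcile the two sections.

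Second, the missing 6-month mean can be recovered from the null hypothesis and the defined difference in the same section, and no analyst would test screening against itself. That is right, and it makes this part a wording error. The sentence is still the decision rule and should be correct.

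Third, the ambiguity would rarely matter if PAE performs as assumed. Under the section 8.3 margin, the chance that p falls between the two thresholds is 0.2% to 4.0% (last column of the second table). At the inferred sizing distance it is 8.0% for the raw difference (89.2 − 81.2). This is fair as to practical reach, but it does not change the error rate at the null boundary, which is what alpha controls.

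Fourth, the 76.9% figure joins a distance built on a 0.263-point margin to the variance of a contrast built on a 10% margin, and no coherent version of the plan has both. It should be read only as a sign that 81.2% does not carry over to the new contrast, not as a forecast that the corrected trial is underpowered.

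**Conclusion.** The concern holds and should be fixed. It is certain that the primary threshold has no stated sidedness, that it differs from the sizing alpha on its natural reading, and that the rule sentence omits the 6-month mean. The size is conditional. On the one-sided reading, type I error is 5.0% against 2.5%, with a band of about 0.35 points (0.36 for the 1.1 × contrast) in which the rule and the 95% interval disagree. On the two-sided reading there is no inflation. If the estimated margin were treated as fixed, the error would be about 3.1% even at a nominal one-sided 0.025. These figures assume 24 pairs, SD 5.7, correlation 0.65 and a paired-t approximation to the planned model.

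**What to change.** Replace the rule in section 8.3 with:

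*PAE is declared non-inferior if the one-sided p-value for the model contrast (mean IPSS at 6 months minus 1.1 × mean IPSS at screening) is <0.025, equivalently if the upper limit of its two-sided 95% CI is below 0.*

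Change the sentence on inconclusive results to the same 0.025 threshold. Report the contrast's interval beside the raw difference. The contrast carries the sampling error of the estimated screening mean, which settles how the margin is handled.

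In section 8.2, recompute power for this contrast with the section 8.3 margin, and state the assumed screening mean and true difference.

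The cost is two sentences, one contrast statement and one power run, with no change to the 30 subjects. The criterion is stricter than a one-sided 0.05 rule. It restores the planned alpha but is not the exact test that was sized, so 81.2% cannot simply be carried over. With the section 8.3 margin and the assumptions in the working, power is 92.2% to 99.8%.
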